### 3.2.2. Secondary Endpoints

#### Immunogenicity

- 50% neutralizing antibody (NT50) geometric mean titer (GMT) against SARS-CoV-2 pseudovirus at baseline, 28 days after the first vaccination and 14 days and 6 months after the second vaccination in all the subjects. The primary analysis will be conducted separately for those who are anti-S IgG seronegative at baseline (no pre-screening for SARS-CoV-2 will be carried out)
- Geometric mean fold rise (GMFR) (from baseline) in NT50 against SARS-CoV-2 pseudovirus at 28 days after the first vaccination, and 14 days and 6 months after the second vaccination
- Percentage of subjects with NT50 seroresponses against SARS-CoV-2 pseudovirus as defined by (1) a  $\geq 4$ -fold increase from baseline, and (2) a  $\geq 10$ -fold increase from baseline at 28 days after the first vaccination and 14 days and 6 months after the second vaccination
- Anti-S IgG GMT at baseline and at 28 days after the first vaccination and 14 days and 6 months after the second vaccination
- GMFR (from baseline) in anti-S IgG GMT at 28 days after the first vaccination and 14 days and 6 months after the second vaccination
- Percentage of subjects with seroresponses in anti-S IgG titer as defined by (1) a  $\geq 4$ -fold increase from baseline, and (2) a  $\geq 10$ -fold increase from baseline, at

28 days after the first vaccination and 14 days and 6 months after the second vaccination

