**Table 2: Phase 1 Dose Escalation Steps – Protocol Table 4**

V1 = Visit 1 (Day 1)

V2 = Visit 2 (Day 8)

PSRT = Protocol Safety Review Team meeting

The PSRT will review blinded safety, reactogenicity and clinical laboratory data accrued on a weekly basis until D43 of the last subject in each phase of the study, then at least once monthly until the end of the study. Subjects will receive 2 doses of assigned IP on D1 and D29 (V1 and V3), and be assessed in clinic for safety and reactogenicity at 7 days after each vaccination (V2 and V4), for safety at 28 days after the second vaccination (V6), and for safety and immunogenicity assessments at baseline (V1), 28 days after the first vaccination (V3) and 14, 168 and 336 days after the second vaccination (V5, V7, and V8, EOS Visit).

An interim analysis of Phase 1 data conducted after the last subject last visit for V6 (D57) will serve as the basis for decisions about down-selection and advancing to Part 2 of the study (Phase 2). Down selection and advancement to Part 2 (Phase 2) will be based on the following parameters:

- Post-dose 2 immunogenicity results at the aggregate treatment level
  - A threshold immune response at Day 43 will be required: the observed seroresponse rate in a treatment group (defined as the percentage of subjects with at least a 4-fold rise from baseline in 80% neutralizing antibody titers) will need to be  $\geq 52\%$  at the LL of the 95% CI for that treatment (vaccine formulation) to be considered for advancement to Phase 2.
- Post-dose 1 and post-dose 2 safety results including all solicited and unsolicited adverse events, serious adverse events, and clinical laboratory results.

The following process will be followed for the decision about down-selection and advancing Part 2 (Phase 2):

- The DSMB will review the unblinded safety data and provide a recommendation to the Sponsor on whether the safety profile is acceptable for advancing a formulation to Phase 2.
- The Sponsor will review the DSMB recommendation in conjunction with the immunogenicity data and select two formulations to advance to Phase 2.

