### 4.2.3. Exclusion Criteria for Enrollment

Participants will be ineligible for this study for any of the following conditions or reasons:

- Use of any investigational medicinal product within 90 days prior to randomization or planned use of such a product during the period of study participation.
- History of administration of any non-study vaccine within 28 days prior to administration of study vaccine or planned within 3 months after enrolment.

**Note:** receipt of any COVID-19 vaccine that is licensed or granted Emergency Use Authorization in Vietnam during the course of study participation is not exclusionary if administered after Visit 5.

- Previous receipt of investigational vaccine for SARS or MERS, or any investigational or licensed vaccine that may have an impact on interpretation of the trial results.
- History of hypersensitivity reaction to any prior vaccination or known hypersensitivity to any component of the study vaccine.
- History of egg or chicken allergy.
- History of angioedema.
- History of anaphylaxis.
- Acute illness (moderate or severe) and/or fever (body temperature measured orally  $\geq 38^{\circ}\text{C}$ ).
- Any abnormal vital sign deemed clinically relevant by the PI.
- Abnormality in screening laboratory test deemed exclusionary by the PI in consultation with the Sponsor.
- A positive serologic test for hepatitis B (HBsAg) or hepatitis C (HCV Ab).
- History of laboratory-confirmed COVID-19 (RT-PCR positive to SARS-CoV-2).
- History of confirmed HIV.
- History of laboratory-confirmed COVID-19.
- History of malignancy, excluding non-melanoma skin and cervical carcinoma in situ.
- Any confirmed or suspected immunosuppressive or immunodeficient state.
- Administration of immunoglobulin or any blood product within 90 days prior to first study injection or planned administration during the study period.
- Administration of any long-acting immune-modifying drugs (e.g., infliximab or rituximab) or the chronic administration (defined as more than 14 days) of immunosuppressants within six months prior to first study injection, or planned administration during the study period (includes systemic corticosteroids at doses equivalent to  $\geq 0.5$  mg/kg/day of prednisone; the use of topical steroids including inhaled and intranasal steroids is permitted).
- History of known disturbance of coagulation or blood disorder that could cause anemia or excess bleeding (e.g, thalassemia, coagulation factor deficiencies).

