#### **4.6. Prior and Concomitant Therapy**

All concomitant medications will be recorded in source documents from Visit 1 (Day 1) through Visit 6 (Day 57). After Visit 6, only those concomitant medications associated with AESI, MAAEs, and SAEs will be recorded. Details on concomitant medications to be recorded include the generic and/or trade name, indication, dosage, regimen, route of administration, and start and end dates of the medication.

The following concomitant medications are prohibited during the study; however, they must not be withheld by the treating physician if clinically indicated to treat a subject:

- Any investigational medicinal product other than the study product
- Administration of immunoglobulins or any blood products
- Administration of any long-acting immune-modifying drugs (e.g., infliximab or rituximab) or the chronic administration (defined as more than 14 days) of immunosuppressive medications (includes systemic corticosteroids at doses equivalent to  $\geq 0.5$  mg/kg/day of prednisone; the use of topical steroids including inhaled and intranasal steroids is permitted).

Use of any prohibited medication must be recorded in the CRF. Whether a subject who uses a prohibited medication will be included in the Per Protocol Population will be evaluated on a case by case basis.

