#### **6.3.5. Per Protocol Population**

All subjects in the exposed population who have no major protocol deviations that are determined to potentially interfere with the immunogenicity assessment of the study product.

This population will serve as the primary analysis population for the immunogenicity endpoints. The population will be adapted by time point to include all eligible subjects' data up to the time of disqualifying protocol deviation. The criteria (e.g., intake of prohibited medication expected to influence the immune response) for exclusion of subjects from the per protocol population, and determination of any exclusions based on a blinded review of the data, will be established before database freeze and lock for both interim and final analyses, respectively.

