**Table 1: Treatment Groups - Protocol Table 3 (see [Table 1](#) in Section [4.1.](#))**

**Table 2: Phase 1 Dose Escalation Step – Protocol Table 4 (see [Table 2](#) in Section [4.1.](#))**

**Table 3: Schedule of Study Visits and Procedures – Protocol Table 5**

VISIT	Screen	V1	V2	V3	V4	V5	V6	V7
Study Day (allowed window in days)	-42 to 1	1	8 (+3)	29 (+3)	36 (+3)	43 (+3)	57 (+7)	197 (+14)
Informed consent	✓							
Demographics	✓							
Medical History	✓							
Concomitant medications A	✓	✓	✓	✓	✓	✓	✓	✓
Eligibility check	✓			~				
Vital signs	✓	✓ ^ ✓	✓	✓ ^ ✓	✓	✓	✓	✓
Complete physical exam	✓							
Targeted physical exam B		✓	✓	✓	✓	✓	✓	✓
Clinical chemistry C	✓		✓		✓			
Hematology D	✓		✓		✓			
Viral serology tests E	✓							
Urine pregnancy test F	✓	✓ ^ ✓		✓				
Unsolicited AEs G	✓	✓	✓	✓	✓	✓	✓	✓
Concomitant medications H	✓		✓	✓	✓	✓	✓	✓
Randomization		✓		~				
Blood for humoral immunity		✓		✓		✓		✓
Blood for CMI I		✓				✓		✓
Administer study product		✓		✓				
Observation/solicited AEs		✓		✓				
Provide Diary Card		✓		✓				
Review Diary Card			✓		✓			
Exit study								
Blood volumes (mL):								
Safety laboratory tests (Phase 1 only)	4		4		4			
HBV and HCV screening	2		0		0			
Humoral immunity		10		10		10		10
Cell-mediated immunity		16				16		16

~ Confirmation

A Evaluations will be conducted twice – before and after vaccinationB After Visit 6, only medications associated with an AESI, MAAE or SAE will be recorded.C Targeted PE will be conducted only in the event of new symptom, sign or, until Visit 6, any new AE; or, after Visit 6, any new AESI, MAAE or SAE.D Serum creatinine, ALT, AST, total bilirubin; only in Phase 1.E WBC count, hemoglobin, platelets; only in Phase 1.F HBsAg, HCV AbG Women of childbearing potential (WOCBP) onlyH After Visit 6, only AESI, MAAEs, and SAEs will be recorded.I After Visit 6, only concomitant medications associated with a newly reported AESI, MAAE or SAE will be recorded Only in subset of subjects in Phase 2

Remark: 1 month = 28 days (4 weeks)

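### Authorised COVID-19 vaccination is allowed after Visit 5, but the SAP has no rule for titres measured after it, so the Day 197 immunogenicity results can mix responses to study and non-study vaccines

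*SAP*

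**What the plan says.** **Permission.** The note in SAP Section 4.2.3 states that a COVID-19 vaccine licensed or under emergency authorisation in Vietnam "during the course of study participation is not exclusionary if administered after Visit 5".

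**Recording.** Section 4.6 states "All concomitant medications will be recorded in source documents from Visit 1 (Day 1) through Visit 6 (Day 57"), and then "After Visit 6, only those concomitant medications associated with AESI, MAAEs, and SAEs will be recorded". A footnote to Table 3 repeats the limit: "After Visit 6, only medications associated with an AESI, MAAE or SAE will be recorded".

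**Prohibited products.** The Section 4.6 list begins with "Any investigational medicinal product other than the study product" and goes on to immunoglobulins and blood products, and to immune-modifying or immunosuppressive drugs. Authorised vaccines are not on it.

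**Populations.** Under Section 6.3.5 a subject's data stay in the per protocol population "up to the time of disqualifying protocol deviation", and Section 4.8 defines a deviation as noncompliance. The full analysis population (6.3.4) has no exclusion for later vaccination. The only serostatus filter in Section 9 is at baseline, and it applies to absolute endpoints, not to GMFR.

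**Endpoints.** Section 3.2.2 lists "Anti-S IgG GMT at baseline and at 28 days after the first vaccination and 14 days and 6 months after the second vaccination", with parallel 6-month endpoints for NT50 and for fold rise and seroresponse in both assays. NT80 is exploratory (3.2.3). Section 4.1 places immunogenicity visits at "14, 168 and 336 days after the second vaccination (V5, V7, and V8, EOS Visit").

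**The concern.** The 6-month titres are there to show how long the response to each formulation lasts. The ELISA in Section 9.2 detects IgG to full-length Spike, whichever product induced it. Section 4.2.3 itself bars entry to people who previously had a vaccine that could affect interpretation, so the plan recognises the problem at baseline. It then permits the same kind of exposure during follow-up without saying what happens to later titres.

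Followed as written, a subject who takes an authorised vaccine between Day 43 and Day 197 contributes a Day 197 titre to every GMT, GMT or GMC ratio, GMFR and seroresponse table, in both populations. Persistence would look better than it is, placebo responses would rise, and real differences between formulations would tend to shrink. If the vaccination was never recorded, the reader could not tell how far this had gone.

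**Working it through.** **1. Visit days.** Dose 2 is on Day 29. 29 + 14 = 43 (Visit 5); 29 + 28 = 57 (Visit 6); 29 + 168 = 197 (Visit 7). These match the SAP.

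**2. Length of the uncovered interval.**
- Visit 5 to Visit 7: 197 − 43 = 154 days.
- Under full recording: 57 − 43 = 14 days.
- After full recording stops: 197 − 57 = 140 days, and 140/154 = 91%.
- With the Table 3 windows (Visit 6 up to Day 64, Visit 7 up to Day 211), the uncovered stretch runs from 197 − 64 = 133 to 211 − 57 = 154 days.

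Even in the 14 covered days, no rule says how a recorded vaccination would be used.

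**3. Does anything exclude the later titre?**
- Prohibited medication (4.6): no, authorised vaccines are not listed.
- Deviation (4.8): a deviation is noncompliance, and a permitted act is not noncompliance. This is inference; the SAP does not say it in words.
- Per protocol cut (6.3.5): it works through deviations, so it is not triggered.
- Full analysis population (6.3.4): no exclusion.
- Serostatus filter (9): baseline only.
- Missing-data rule (6.5): it covers absent results, not altered ones.

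**4. Scale, on assumed inputs.** The SAP gives neither uptake nor boost size. Let a share f of an arm have its titre raised R-fold. The mean log titre rises by f × log R, so the GMT is multiplied by R^f.

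- f = 10%: 1.15 (R = 4), 1.26 (R = 10), 1.41 (R = 30)
- f = 25%: 1.41, 1.78, 2.34
- f = 50%: 2.00, 3.16, 5.48
- f = 80%: 3.03, 6.31, 15.19

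For comparison, take the Section 5 planning values of log10 SD 0.5 and n = 22 evaluable. The 95% half-width is 10^(t(0.975, 21) × 0.5/√22), so a GMT is known to about ×/÷ 1.67. An uptake of 25% with R = 10 shifts the GMT by 1.78, more than that margin; 10% with R = 10 shifts it by 1.26, less than the margin.

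*Ratios.* If vaccinated subjects reach the same level in all arms and uptake is equal, a true 2-fold GMT ratio becomes 2^(1 − f): 1.87, 1.41 and 1.15 at f = 10%, 50% and 80%.

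*Seroresponse.* If every vaccinated subject responds, a true rate p becomes p + f(1 − p). With p = 30% and f = 25% this is 0.30 + 0.25 × 0.70 = 47.5%. With p = 0, as might hold in placebo, it is f.

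**The case against.** The strongest answer is that the SAP has not closed the door. Section 6.3.5 leaves the per protocol criteria to be set before freeze and lock after blinded review, offers prohibited medication only as an example, and adapts the population by time point. The Table 7 shell has a row for Day 197 exclusions with reasons. A criterion for non-study vaccination could still be added. That stands, but such a criterion needs a record of who was vaccinated and when, and the SAP neither states the criterion nor secures the record.

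A second answer is that data collection belongs to the protocol and CRF, which are not shown. The recording limit is worded for concomitant medications, and vaccinations may be captured elsewhere. That also stands, so the 140-day gap is conditional. The missing analysis rule is not.

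Third, keeping all observed titres in the full analysis population is a legitimate summary regardless of later vaccination. Agreed; only the per protocol handling and the labelling are at issue.

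Fourth, arms are randomised and observer-blind at one centre, with placebo spread across the four cohorts. A large uptake gap between arms is therefore not well motivated, and equal uptake, which dilutes differences, is the more natural case.

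Two stronger readings are tempting. A reader might infer that the Day 197 data are beyond repair. The documents do not support that, because the criteria are still open and vaccination history can be taken retrospectively from vaccination records. A reader might also infer that formulation selection is compromised. It is not: the 52% gate uses Day 43, and the permission begins only after that visit.

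**Conclusion.** The point holds as a gap in how Day 197 results are handled. The SAP permits a foreseeable event that changes the measured outcome, gives no rule for titres after it, and on its own text stops recording it for most of the interval unless an adverse event is attached. The affected results are the Day 197 (and any 12-month) GMT, GMT or GMC ratio, GMFR and seroresponse summaries for NT50, NT80 and anti-S IgG. These are descriptive secondary and exploratory outputs. Primary safety, Day 29, Day 43 and the selection gate are untouched.

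The size cannot be stated. The multipliers above show only that modest uptake could matter at these group sizes. The conclusion rests on two conditions: that a permitted vaccination is not treated as a deviation, which is a sound inference but not stated text, and, for the recording gap only, that the protocol or CRF does not collect vaccination separately. It should be fixed before lock.

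**What to change.** 1. **Record.** Before lock, confirm that the product and date of any non-study COVID-19 vaccine are held for every subject through the last visit. If not, collect them, for example at Visit 7 from vaccination records, and align Section 4.6 and the Table 3 footnotes.
2. **Analyse.** In Sections 6.3.5 and 9, exclude per protocol immunogenicity results from the date of the first non-study COVID-19 vaccine. Keep the full analysis population as the all-data version, labelled as including other vaccines.
3. **Report.** Show the number and timing of these vaccinations by arm next to the Day 197 tables.

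The permission itself need not change. The cost is at most one CRF item plus SAP wording; if the data already exist, wording alone is enough. The statistical price is fewer evaluable subjects at Day 197 and possible selection, because exclusion depends on a choice made after randomisation and Section 6.5 treats absent results as randomly missing. That is the reason to show both versions.

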## 4.3. Study Product

### 4.3.1. Product Descriptions

NDV-HXP-S is an inactivated NDV chimera expressing a trimeric pre-fusion form of the SARS-CoV-2 S protein that contains six proline mutations (HexaPro). The vaccine is a clear and slightly opalescent liquid.

All study vaccine products to be administered on a given day (based on the study stage) will be formulated separately by the assigned site staff under aseptic conditions at the start of the clinic day. A detailed mixing procedure will be provided in the Pharmacy Manual or SOP for study product preparation. Each vaccine product will be formulated by filling a 4 ml (4R) [with the height of 46 mm and diameter of 16/1 mm] USP Type I glass vial with bulk drug substance, bulk adjuvant (if indicated based on formulation) and phosphate-buffered saline (PBS) to allow for five 0.5 ml doses per vial, as well as sufficient residual volume for possible dose verification. Each vial label will include the following information: name of the medicinal product, composition, fill volume, route of administration, lot number, manufacturing date, storage condition, and a cautionary statement (“For Clinical Trial Use Only”).

The placebo control is PBS (pH 7.2), manufactured by IVAC and tested by National Institute for Control of Vaccines and Biological (NICBV).

### 4.3.2. Identity of Investigational Product

#### Investigational Vaccine:

Inactivated Newcastle Disease Virus (NDV) chimera expressing a trimeric pre-fusion form of the SARS-CoV-2 Spike (S) protein that contains six proline mutations (HexaPro, HXP); for intramuscular (IM) administration. One formulation of NDV-HXP-S evaluated in this study includes 1.5 mg of the adjuvant CpG 1018 (a 22-mer phosphorothioate-linked oligodeoxynucleotide).

#### Placebo:

Phosphate-buffered saline (PBS); for IM administration

#### **4.4. Method of Assigning Participants to Treatment Groups (Randomization)**

The randomization scheme was generated and maintained by Center of Excellence for Biomedical and Public Health Informatics (BIOPHICS).

Randomization for Part 1 (Phase 1) will be conducted after accumulation of 120 eligible subjects. Randomization will be stratified by gender and age (less than 40 years old and 40 to 59 years old, with approximately 50% of subjects in each age stratum). This is to ensure the groups are as similar (homogenous) as possible to ensure the down-selection of formulations is not biased by differences in demographic characteristics of the groups (such as age and gender). Randomization details will be outlined in a Randomization Plan prior to study initiation.

Each group will be divided into two subgroups, a sentinel subgroup (n=6) and a larger subgroup (n=24) that includes the remaining subjects to be evaluated at that dose level (or for that formulation in the case of the one adjuvanted treatment group). Initially, a sentinel subgroup of 6 subjects will be randomized to receive NDV-HXP-S 1  $\mu$ g or placebo in a 5:1 ratio. Sentinel subjects will be monitored for reactogenicity and safety through Day 8 (Visit 2), including for the initial 24 hours post-injection in clinic. If the PSRT has no safety concerns based on blinded review of all safety data, including clinical laboratory results, through Visit 2, the second subgroup of 24 subjects will be randomized to receive NDV-HXP-S 1  $\mu$ g or placebo at the same ratio; on the same day, the sentinel subgroup (n=6) for the second dose level to be evaluated (NDV-HXP-S 3  $\mu$ g) can be randomized to receive study vaccine or placebo in a 5:1 ratio, and so on for the subsequent dose level and formulation (see [Table 2](#)). The same procedure will be used for the NDV-HXP-S 10  $\mu$ g and NDV-HXP-S 1  $\mu$ g + CpG arms for a total of n=25 in each active group and n=20 in the placebo group. Randomization will be stratified by age (less than 40 years old and 40 to 59 years old) and gender with approximately 25% of subjects in each age & gender stratum.

#### **4.5. Blinding**

A limited number of appropriately trained, unblinded study staff, including the site pharmacist, will be responsible for preparing study products (in accordance with the randomly determined assignment), administering the study vaccine, and handling all drug accountability procedures. These personnel will not participate in the other aspects of the clinical trial, to help ensure the integrity of the blind at the site. The unblinded staff will not reveal subjects' randomization assignments to subjects, or staff associated with the Sponsor, CRO, or site.

Randomization data are kept strictly confidential, and should be accessible only to authorized persons, until the time of unblinding.

##### **4.5.1. Unblinding Procedure**

In the event of a medical emergency, the PI/designee may require that the blind be broken

for the subject experiencing the emergency when knowledge of the subject's treatment assignment may influence the subject's clinical care. Every effort will be made not to unblind the subject unless it is considered absolutely necessary for the welfare of the subject. Prior to unblinding, the investigator is encouraged (to the extent possible, without jeopardizing the subject's health) to contact the Sponsor (or designee) to discuss the decision to break the blind.

Unblinding will occur according to the emergency unblinding SOP, to which there will be 24-hour access. Documentation of the unblinding event will be captured by the unblinded staff. The PI/designee will be expected to provide a rationale for the necessity of unblinding, based on the expectation that knowledge of the subject's treatment assignment will have a meaningful impact on the subject's medical care in the short term. If a subject's treatment assignment is unblinded, the subject will remain in the study and continue with protocol-defined study visits and procedures, unless there is another reason for subject discontinuation. The decision to unblind will be communicated to all regulatory bodies as required. At the end of the study, documentation of all unblinded subjects (and the rationale for unblinding) will be incorporated into the TMF.

